2.3 Secondary Objective

CONFIDENTIAL

This document is confidential. Do not disclose or use except as authorized.

The secondary objectives are:

- To determine the clinical improvement in clinician-reported outcome measures achieved by treatment with topical compound dexamethasone at 0.5 mg/5 mL in Mucolox™ compared to dexamethasone 0.5mg/5ml solution alone.
- To assess the tolerability of oral lichen planus as measured with the chronic oral mucosal diseases quality of life questionnaire (COMDQLQ).

2.4 Hypothesis

Dexamethasone solution (0.5mg/5ml) in Mucolox™ when swished for 5 minutes and expectorated three times daily, is *well-tolerated* and *more effective* than dexamethasone solution (0.5 mg/5 mL) alone in the management of oral lichen planus.

2.5 Specific Aim

In order to evaluate the hypothesis, the specific aim for this study is:

- 2.5.1 To compare the clinical outcome with a primary endpoint of reduction in oral symptoms between patients treated with dexamethasone 0.5mg/5ml solution in Mucolox™ (group A) and patients treated with topical dexamethasone 0.5mg/5ml solution only (group B).

3. SUBJECT SELECTION

3.1 Eligibility Criteria

- 3.1.1 Age 18 years and older.
- 3.1.2 Patients with symptomatic oral lichen planus (worst VAS sensitivity score ≥ 7 over the last week).
- 3.1.3 Ability to understand and the willingness to sign a written informed consent document.

3.2 Exclusion Criteria

- 3.2.1 Patients already on topical or systemic steroids.
- 3.2.2 Inability to comply with study instructions.
- 3.2.3 Uncontrolled intercurrent illness or psychiatric illness/social situations that would limit compliance with study requirements.
- 3.2.4 VAS sensitivity score < 7 .
- 3.2.5 Pregnant women. A urine pregnancy test will be performed for women of child bearing potential.

CONFIDENTIAL

This document is confidential. Do not disclose or use except as authorized.

3.2.6 Allergy to fluconazole, clotrimazole or nystatin.

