4. SUBJECT ENROLLMENT

The Division of Oral Medicine and Dentistry at Brigham and Women's Hospital is a major referral center for oral medicine patients including patients with oral lichen planus. Clinical diagnosis of oral lichen planus will be made by the patient's oral medicine specialist. Patients with a confirmed clinical diagnosis of oral lichen planus and with oral symptoms (defined as the worst VAS sensitivity score ≥ 7 over the last week) will be eligible to participate in this study. Potentially eligible subjects will be screened by one of the investigators by asking patients to rate their worst oral pain score (0-10) over the previous week (see Appendix). Those answering with at least a score of "7" (1/10) and that meet all other eligibility requirements (see section 3.0) will be eligible for enrollment. All patients (and/or parents/guardians) will sign informed consent for participation. All patients will be offered the opportunity to take home the consent form, and call back if they wish to participate.

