4.1 Procedures for obtaining informed consent

All patients will sign an informed consent. Patients will be informed that they have equal chances of being assigned to one of two groups. Patients will be told what personal identifying information will need to be collected, and the privacy rights of study participants will be explained. The consenting physician will ensure that the patient is given full and adequate oral and written information about the nature, purpose, and possible risks and benefits of the study, with the clear understanding that participation is optional. Patients will be encouraged to ask questions and will have the opportunity to take the consent form with them and review before making a decision whether or not to participate. Patients will also be notified that they are free to discontinue participation in the study at any time. By signing the consent form, potential subjects agree to participate in the study. If consent is withdrawn during the study, no further measurements will be conducted.

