5. STUDY PROCEDURES

Potentially eligible subjects will be screened by one of the investigators by asking patients to rate their worst oral pain or pain score (0-10) over the previous week (see Appendix). Those answering with at

CONFIDENTIAL

This document is confidential. Do not disclose or use except as authorized.

least a score of “7” (1/10) and that meet all other eligibility requirements (see Section 3) will be eligible for enrollment. All patients will sign informed consent for study participation. Each study visit is anticipated to take approximately 45 minutes. A urine pregnancy test will be performed for women of child bearing potential.

There is no financial compensation for participating in this study. Treatment will be administered on an outpatient basis. Study medication will be prescribed by authorized study staff physicians and filled by the BWH Investigational Pharmacy at no expense for the patient. No investigational or commercial agents or therapies other than those described below may be administered with the intent to treat the participant’s oral lichen planus.

Subjects will be evaluated clinically at baseline before starting treatment and at the end of the four-week period, for a total of two visits. Comprehensive subjective and objective data will be collected (Appendix 3 & 4) and intraoral photographs will be obtained. Oral mucosal disease will be evaluated using both patient reported (questions/visual analog scales) and clinician assessed measures.

Subjects will be prescribed compound dexamethasone 0.5mg/5ml solution in Mucolox™ (ARM A) or dexamethasone 0.5mg/5ml solution only (ARM B). All subjects will also receive a prescription for fluconazole 200 mg tablets once-a-week as prophylactic antifungal therapy. Any subjects that are already taking an antifungal oral medication at the time of the study enrollment will continue their prescribed medication and will not need to take the additional weekly fluconazole dose. Subjects will return for evaluation after four weeks at which time the study end-points will be assessed.

Clotrimazole or Nystatin will be prescribed as an alternative antifungal drug in the event of fluconazole allergy.

If there is worsening of oral lichen planus that requires initiation of new immunomodulatory medications (systemic or topical), patients will remain on treatment, but will be regarded as unevaluable for the primary endpoint.

	Day 1 (baseline)	Day 28 ± 5 days (end of study)

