5.5 General Concomitant Medication and Supportive Care Guidelines

There will be no restrictions on concomitant medications or supportive care measures.

All subjects will be treated with fluconazole 200 mg tablets once-a-week dosing for prophylaxis as topical steroid therapy may increase the risk of candidiasis. This is typically very effective at preventing candidiasis in susceptible patients, and since there are no interim clinical visits, this will minimize the risk of secondary infection, which if not detected early, could confound the results at the week 4 evaluation. A single weekly dose of fluconazole is not sufficient to have an impact on therapeutic levels of other medications. Fluconazole is a pregnancy category D drug. A such, pregnant women will be excluded from this study.

Any subjects that are already taking a systemic antifungal medication at the time of study enrollment will continue their prescribed medication and will not need to take the additional weekly fluconazole dose.

Clotrimazole or nystatin will be prescribed as an alternative antifungal drug in the event of fluconazole

CONFIDENTIAL

This document is confidential. Do not disclose or use except as authorized.

allergy. Clotrimazole 10 mg troche (lozenge) to be dissolved in the mouth four times a day for four weeks; or nystatin 100,000 unit/mL oral suspension to rinse for one minute, swish and spit, four times a day for four weeks.

Possible side effects of fluconazole include nausea, vomiting and headache. Possible side effects of nystatin oral suspension include rash, diarrhea, nausea, oral irritation, vomiting. Possible side effects of clotrimazole troche (lozenge) include abnormal sensation in the mouth, loss of appetite, diarrhea, nausea, vomiting, abnormal liver function tests.

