5.6 Criteria for Taking a Participant Off Protocol Therapy

Subjects will be taken off protocol therapy for any of the following reasons:

- If the principal investigator feels it is in their best interest
- If the subject cannot tolerate the study rinses
- Intercurrent illness that prevents further administration of treatment
- Unacceptable adverse event(s)
- Participant demonstrates an inability or unwillingness to comply with the oral medication regimen and/or documentation requirements
- Participant decides to withdraw from the protocol therapy
- General or specific changes in the participant's condition render the participant unacceptable for further treatment in the judgment of the treating investigator

Participants will be removed from the protocol therapy when any of these criteria apply. The reason for removal from protocol therapy, and the date the participant was removed, must be documented in the case report form (CRF). Alternative care options will be discussed with the participant.

Subjects may be removed from the study in favor of clinical care should their symptoms worsen or should they have an adverse reaction to the study drug.

In the event of unusual or life-threatening complications, treating investigators must immediately notify the Overall PI [name], PhD, MPH at [contact] ([name]).

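### Section 3.2 excludes current pregnancy because of fluconazole, but the visible criteria do not ask women of child-bearing potential to avoid conceiving during the four-week course

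*Combined protocol and SAP*

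**What the plan says.** Criterion 3.2.5 in section 3.2 (Exclusion Criteria) reads "Pregnant women. A urine pregnancy test will be performed for women of child bearing potential". Section 5 (Study Procedures) mentions the test again, with no day and no repeat. Section 5.5 supplies the reason: "Fluconazole is a pregnancy category D drug. A such, pregnant women will be excluded from this study".

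The exposure is set out in section 5: "All subjects will also receive a prescription for fluconazole 200 mg tablets once-a-week as prophylactic antifungal therapy". There are two exceptions. A subject already on an antifungal stays on it, and clotrimazole or nystatin replaces fluconazole in case of allergy, although 3.2.6 already excludes that allergy. Treatment lasts four weeks, with visits only at baseline and week 4. Section 5.5 justifies prophylaxis partly "since there are no interim clinical visits".

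Section 4 makes the section 3 list operative: patients with the required symptom score who "meet all other eligibility requirements (see section 3.0) will be eligible for enrollment". Section 5 says the same.

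Three provisions bear on pregnancy risk without naming it:
- Section 4.1 commits the consenting physician to giving "full and adequate oral and written information about the nature, purpose, and possible risks and benefits of the study".
- Section 6.3.1 asks subjects to raise adverse events or concerns with study staff.
- Section 5.6 lists grounds for stopping therapy. They include the principal investigator's view of the subject's best interest, and changes in the participant's "condition render the participant unacceptable for further treatment in the judgment of the treating investigator". It adds: "Participants will be removed from the protocol therapy when any of these criteria apply".

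**The concern.** The protocol's own premise is that fluconazole in pregnancy is reason enough to keep a woman out. That reason applies on every day she takes the drug. The criterion built on it applies only to a woman who is already pregnant, and a test shows status on one day. A woman who tests negative and says she is trying to conceive meets every visible criterion and, unless she already takes an antifungal, is to be prescribed fluconazole. At stake is an avoidable fetal exposure that the protocol itself regards as unacceptable. Nothing in the estimation or testing of the treatment effect depends on it.

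**Working it through.** The plan gives no figure to reproduce. The check is a comparison of texts, followed by a bound on exposure.

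**1. Does any visible criterion cover planned pregnancy?**
- Section 3.1 has three inclusion criteria: age, symptom score and consent. None concerns pregnancy.
- Section 3.2 has six exclusions: current steroids, inability to comply, intercurrent or psychiatric illness, low symptom score, pregnancy, and antifungal allergy. Only 3.2.5 concerns pregnancy, and it concerns current pregnancy.
- The compliance criteria (3.2.2, 3.2.3) do not fill the gap, because no visible study instruction mentions contraception or avoiding pregnancy.

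**2. Does any other visible text supply it?**
- The patient instructions in Appendix 1 cover only the rinse.
- The visible schedule rows and the Visit 1 form have no line for a pregnancy test or for an agreement to avoid pregnancy.
- Section 5.6 does not name pregnancy, though two of its grounds could be applied to it.
- Clotrimazole and nystatin are reserved for fluconazole allergy, so they are not a written route for a woman planning pregnancy.

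**3. How much drug could follow a conception?**

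Inputs: 200 mg once weekly (sections 5 and 5.5) over a 28-day treatment period (section 5.2). Assumptions: the test and the first dose are both on day 1, with conception after that. Section 5.5 states no tablet count. Weekly dosing over four weeks gives doses on days 1, 8, 15 and 22, so 4 × 200 = 800 mg in all.

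| Conception in | Doses still to come | Amount |
|---|---|---|
| Week 1 (days 1–7) | 3 | 3 × 200 = 600 mg |
| Week 2 (days 8–14) | 2 | 2 × 200 = 400 mg |
| Week 3 (days 15–21) | 1 | 1 × 200 = 200 mg |
| Week 4 (days 22–28) | 0 | 0 mg |

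The ceiling is 600 mg under these assumptions. It rests on them: if the first dose came some days after the test and conception fell between the two, all four doses (800 mg) would follow.

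**4. How many women?**

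The documents do not say. As an illustration only, section 1.1 puts the frequency in middle-aged women at twice that in men. If the same ratio held among the 24 subjects, 24 × 2/3 = 16 would be women. If 10% to 30% of those were of child-bearing potential (an assumed range with no source in the documents), that would be 1.6 to 4.8, or about 2 to 5. Those planning pregnancy within the four weeks would be fewer, possibly none. No conception rate or risk per dose is given, so none of these figures measures harm.

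**The case against.** The strongest reply is that the finding rests on an absence in a file from which the consent pages were removed. Those pages may well ask for contraception, and section 6.3.2 puts all participant information before the IRB. This stands as a limit on what can be said about what subjects are told. It does not alter the eligibility rule, because section 3 is fully visible and does not contain the condition.

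Second, being eligible does not oblige a physician to enrol a woman who says she is trying to conceive, or to prescribe fluconazole for her. That is correct. A reader might infer that the plan requires such a woman to be treated; the documents do not support this. They only leave her admissible.

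Third, the best-interest ground in section 5.6 is broad. It needs neither an adverse event nor a confirmed pregnancy, and could be used for a suspected pregnancy or a disclosed intention to conceive. That also stands, so it would be wrong to say that only a recognised pregnancy can be acted on. But the ground is discretionary, applies after entry, and with no interim visit depends on the subject raising the matter.

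Fourth, one could instead offer nystatin or clotrimazole to women planning pregnancy and exclude nobody. That is a fair alternative. However, it would need its own amendment, the documents say nothing about those drugs in pregnancy, and it would put these subjects on a four-times-daily oral antifungal unlike the rest.

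**Conclusion.** The point holds as a cheap, small improvement to patient safety. The visible eligibility list applies the fluconazole rationale to current pregnancy only and leaves eligible a woman of child-bearing potential who tests negative and plans to conceive during the course. Risk information, reporting of concerns and section 5.6 reduce the risk, but none makes avoiding conception a condition of entry.

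Two stronger readings should be resisted. A reader might conclude that subjects are never told to avoid pregnancy; without the consent form, that cannot be said. A reader might also conclude that the trial lacks any means of stopping fluconazole in such a case; section 5.6 provides one, at the investigator's discretion.

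At most 3 doses (600 mg) would follow a conception, if the test and first dose are both on day 1. An entry test is the likeliest reading of sections 3.2 and 5, but its timing is not stated, and a test at week 4 would detect a pregnancy without preventing exposure. The number of women concerned is unknown and probably very few. Endpoints, power and analysis are unaffected.

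**What to change.** Extend 3.2.5 to exclude women of child-bearing potential who plan pregnancy, or who will not agree to avoid it, during the four-week fluconazole course. Record that agreement at Visit 1. Give subjects a written line, with the fluconazole prescription, telling them to stop fluconazole and call the site if they suspect pregnancy, with removal from therapy under section 5.6. If the consent form already says this, align 3.2.5 with it.

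The cost is one sentence in the criteria, one written line for subjects, one entry on the Visit 1 form and a short IRB-approved amendment (section 6.3.2). No test or visit is added. The downside is possibly a very few extra exclusions. The change will not catch a pregnancy too early for the entry test to show, unless the subject later suspects it.

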3.3 Inclusion of Women and Minorities

Both men and women of all races and ethnic groups are eligible for this trial.

4. SUBJECT ENROLLMENT

The Division of Oral Medicine and Dentistry at Brigham and Women's Hospital is a major referral center for oral medicine patients including patients with oral lichen planus. Clinical diagnosis of oral lichen planus will be made by the patient's oral medicine specialist. Patients with a confirmed clinical diagnosis of oral lichen planus and with oral symptoms (defined as the worst VAS sensitivity score ≥ 7 over the last week) will be eligible to participate in this study. Potentially eligible subjects will be screened by one of the investigators by asking patients to rate their worst oral pain score (0-10) over the previous week (see Appendix). Those answering with at least a score of "7" (1/10) and that meet all other eligibility requirements (see section 3.0) will be eligible for enrollment. All patients (and/or parents/guardians) will sign informed consent for participation. All patients will be offered the opportunity to take home the consent form, and call back if they wish to participate.

4.1 Procedures for obtaining informed consent

All patients will sign an informed consent. Patients will be informed that they have equal chances of being assigned to one of two groups. Patients will be told what personal identifying information will need to be collected, and the privacy rights of study participants will be explained. The consenting physician will ensure that the patient is given full and adequate oral and written information about the nature, purpose, and possible risks and benefits of the study, with the clear understanding that participation is optional. Patients will be encouraged to ask questions and will have the opportunity to take the consent form with them and review before making a decision whether or not to participate. Patients will also be notified that they are free to discontinue participation in the study at any time. By signing the consent form, potential subjects agree to participate in the study. If consent is withdrawn during the study, no further measurements will be conducted.

4.2 Treatment assignment and randomization

Randomization will be predetermined by a computer generated list and coordinated by the BWH Investigational Pharmacy. Patients will be assigned to one of two groups: 1) Arm A: commercial dexamethasone 0.5mg/5ml solution in Mucolox™ or 2) dexamethasone 0.5mg/5ml solution only (ARM B).

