2.2 Primary Objective

The primary objective of this study is to determine the clinical efficacy and tolerability of compound dexamethasone at 0.5 mg/5 mL in Mucolox™ for the treatment of oral lichen planus as measured by a reduction in oral symptoms between patients treated with commercial dexamethasone 0.5mg/5ml solution in Mucolox™ (group A) and patients treated with topical dexamethasone 0.5mg/5ml solution only (group B).

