5.3 Study Agents Administration

The Investigator or co-investigators will prescribe the study drug in the clinic via Epic and instruct the patient on study drug use. Both dexamethasone compound 0.5mg/5ml solution in Mucolox™ and dexamethasone solution will be dosed topically at a concentration of 0.5 mg/5mL.

A four week supply will be dispensed. The treatment instructions will be to rinse and spit (NOT swallow) with one teaspoon (5 mL) of the solution, three times a day for 5 minutes at a time, and not to eat or drink for 15 minutes afterwards. Subjects will maintain a diary and record each dose, the length of time rinsing, and any adverse effects.

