11.1.4 Availability

Compound dexamethasone solution in Mucolox™ will be dosed at a concentration of 0.5 mg/5mL and dispensed through the BWH Investigational Pharmacy. The prescription for the patients in ARM B (dexamethasone) will also be dispensed through the BWH Investigational Pharmacy.

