11.2 Dexamethasone solution

11.2.1 Description

Dexamethasone (NDC 00054-3177-63; Roxane Laboratories, Columbus, OH 43216-6532) is a synthetic adrenocortical steroid commercially available as a 0.5mg/5mL solution. It is stable in air and practically insoluble in water.

- The molecular weight is 392.47.
- The molecular formula is $C_{22}H_{29}FO_5$
- The structural formula is:

Each 5 mL of oral solution contains 0.5 mg of dexamethasone and citric acid, disodium edetate, flavoring, glycerin, methylparaben, propylene glycol, propylparaben, sorbitol and water.

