Appendix 1: Patient instructions

Appendix 2: Treatment diary

Appendix 3: Visit #1 CRF

Appendix 4: Visit #2 CRF

Appendix 5: COMDQLQ

CONFIDENTIAL

This document is confidential. Do not disclose or use except as authorized.

INSTRUCTIONS FOR PREPARING & USING YOUR TOPICAL SOLUTION

WHAT YOU WILL RECEIVE

- One 480 mL bottle of concentrated solution (5 mg/5 mL)

USING YOUR SOLUTION

You will be rinsing with your solution **3 times per day**.

1. Gently shake the bottle of solution.
2. Pour 5 mL of solution into the dosing cups provided.
3. Swish the solution in your mouth for 5 minutes, then spit – DO NOT SWALLOW!
4. Do not eat or drink for 15 minutes after rinsing.

CONFIDENTIAL

This document is confidential. Do not disclose or use except as authorized.

	13								
	14								

Week	Day/Date	Rinse #1 (check/fill)		Rinse #2 (check/fill)		Rinse #3 (check/fill)		From a scale 0-10, how would you rate your mouth sensitivity today?	Comments
		5 min	Other*	5 min	Other*	5 min	Other*		
3	15								
	16								
	17								
	18								
	19								
	20								
	21								
4	22								
	23								
	24								

CONFIDENTIAL

This document is confidential. Do not disclose or use except as authorized.

	25								
	26								
	27								
	28								

CONFIDENTIAL

This document is confidential. Do not disclose or use except as authorized.

**DEXAMETHASONE RINSE AND MUCOLOX™ FOR THE TREATMENT OF ORAL
LICHEN PLANUS**

VISIT #1

Subject Name _____

Medical Record Number _____

Date of Visit _____

[figure not shown]
[figure not shown]
SUBJECTIVE DATA (Over last two weeks unless specified)

MUCOSAL PATHOLOGY

1. Does your mouth hurt now? Y/N

2. Does it hurt to swallow food or drink? Y/N

3. How would you rate your worst mouth sensitivity over the last week?

No sensitivity

Worst sensitivity

CONFIDENTIAL

This document is confidential. Do not disclose or use except as authorized.

[figure not shown]
[figure not shown]
4. Do you avoid any foods because they make your mouth hurt?

- 0 = Not at all
- 1 = Slightly
- 2 = Moderately
- 3 = Quite a bit
- 4 = Extremely

If “yes”, what types of foods?

- a. Spicy foods
- b. Acidic foods
- c. Salty foods
- d. Hard/crunchy/crusty foods
- e. Other:

5. Do you feel that your oral intake (what you eat) is limited by your oral condition? Y/N

Not limited at all

Severely limited

Score: _____

If “Yes”, how limited do you feel it is?

- a. Partial limitation
- b. Severe limitation

6. Have you been bothered by ulcers in the mouth?

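### The protocol contradicts itself on study-drug strength: the patient sheet gives ten times the strength in the body, and Arm A's two descriptions agree only if dexamethasone is added at compounding, which is not described

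*Combined protocol and SAP*

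**What the plan says.** **Strength in the protocol body.** The regimen table in Section 5.2 has the same entry for both arms: 0.1 mg/mL, 0.5 mg per 5 mL rinse, 1.5 mg a day. Section 5.3 covers both products in one sentence, ending "dexamethasone solution will be dosed topically at a concentration of 0.5 mg/5mL". Section 11.1.4 says of the Arm A product that it "will be dosed at a concentration of 0.5 mg/5mL and dispensed through the BWH Investigational Pharmacy". Sections 11.1.5 (Arm A) and 11.2.6 (Arm B) each specify a 480 mL bottle at 0.5 mg/5 mL. Sections 8.1 and 10.4 derive a weekly maximum of 10.5 mg from this strength.

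**Strength on the patient sheet.** Appendix 1 tells the patient to expect "One 480 mL bottle of concentrated solution (5 mg/5 mL". The sheet is titled as covering preparation as well as use, but its steps are to shake the bottle, pour 5 mL, swish, spit, and wait before eating or drinking. None of them dilutes the solution. The sheet names no arm, and Sections 11.1.5 and 11.2.6 both refer to it.

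**What Arm A is made from.** Section 4.2 defines "Arm A: commercial dexamethasone 0.5mg/5ml solution in Mucolox". Section 2.2 also speaks of "patients treated with commercial dexamethasone 0.5mg/5ml solution in Mucolox", although earlier in the same sentence it calls the product "compound dexamethasone at 0.5 mg/5 mL in Mucolox". Section 11.2.1 says that dexamethasone "is a synthetic adrenocortical steroid commercially available as a 0.5mg/5mL solution". Section 11.1.5, headed as preparation, lists only the kit contents. Section 11.1.2, on compatibility, is marked not applicable. No section gives a mixing ratio, a vehicle volume or a second source of dexamethasone.

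**The concern.** Two conflicts need to be kept apart.

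The first is between the patient sheet and the body. It is a factor of ten, applies to both arms, and sits in the one document that patients follow at home. The argument in Sections 8.1 and 10.4 that systemic effects are not expected uses the lower figure for its worst case.

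The second is between two descriptions of Arm A. The hypothesis (Section 2.4) and the specific aim (Section 2.5.1) compare the same strength with and without Mucolox, so that the vehicle is the only difference. Mucolox is a gel containing water and glycerin (Sections 1.3 and 11.1.1), so it takes up volume. Putting a 0.5 mg/5 mL solution into it lowers the strength unless more drug goes in. If that happened, the arms would differ in dose as well as vehicle. An absence of difference could then reflect a vehicle benefit cancelled by a lower dose.

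**Working it through.** **Inputs from the documents.** Rinse volume 5 mL, three rinses a day, seven days a week (5.2). Strength in the body 0.5 mg/5 mL = 0.1 mg/mL (5.2, 5.3, 11.1.4, 11.1.5, 11.2.6). Commercial product 0.5 mg/5 mL = 0.1 mg/mL (11.2.1). Patient sheet 5 mg/5 mL = 1 mg/mL (Appendix 1). Bottle 480 mL (11.1.5, 11.2.6, Appendix 1).

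**Step 1: reproduce the plan's figure.** 5 mL × 0.1 mg/mL = 0.5 mg per rinse; × 3 = 1.5 mg a day; × 7 = 10.5 mg a week. This matches Section 5.2 and the maximum in Sections 8.1 and 10.4. The bracketed working in 8.1 and 10.4 ends in grams where its own arithmetic gives milligrams; that is a unit slip.

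**Step 2: the patient sheet.** 5 mL × 1 mg/mL = 5 mg per rinse; × 3 = 15 mg a day; × 7 = 105 mg a week. Ratio to the body: 105 / 10.5 = 10. One bottle would hold 480 × 1 = 480 mg, against 480 × 0.1 = 48 mg in the body.

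**Step 3: mass balance for Arm A.** Let v be the share of the finished volume that is Mucolox, and assume that the commercial solution is the only drug source. Then

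dose per rinse = 5 mL × 0.1 mg/mL × (1 − v) = 0.5 × (1 − v) mg.

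The documents do not give v, so the table shows an assumed range. The last column is the dexamethasone that another source would have to supply to bring a 480 mL bottle back to 48 mg, which is 48 × v.

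| Assumed v | Arm A, mg per rinse | Arm A, mg per day | Arm B, mg per rinse | Extra drug needed per bottle, mg |
|---|---|---|---|---|
| 10% | 0.45 | 1.35 | 0.5 | 4.8 |
| 25% | 0.375 | 1.125 | 0.5 | 12 |
| 50% | 0.25 | 0.75 | 0.5 | 24 |
| 75% | 0.125 | 0.375 | 0.5 | 36 |

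Seen from the bottle: 48 mg at 0.1 mg/mL needs 48 / 0.1 = 480 mL of the commercial solution, which fills the bottle and leaves no room for vehicle. The two descriptions of Arm A therefore agree only if v = 0, in which case there is no Mucolox, or if dexamethasone comes from a further source.

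**Step 4: sample size.** The calculation in Section 6.2 uses a difference of 2.0 points and a standard deviation of 1.4. Strength does not enter it, so the 12 per arm is not affected by this point.

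**The case against.** The best defence concerns Arm A. Section 2.2 uses both the commercial and the compound wording for one product in a single sentence, most other sections use only the compound wording, and every explicit dosing statement in the body gives the arms equal strength. On that reading, the commercial phrase is a loose name for the finished strength and not a recipe. A pharmacy would also be expected to work from the regimen table and Section 11.1, not from the randomization paragraph. This defence stands in part: it makes equal strength the evident intention. It does not say how equal strength is reached, since the commercial solution is the only dexamethasone source the protocol describes.

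Three stronger readings are tempting, and the documents do not support them.

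- A reader might infer that the two descriptions of Arm A are flatly incompatible, or that Arm A is in fact weaker. Both inferences need the commercial solution to be the sole drug source, which no section states. The vehicle fractions above are illustrations, not evidence of an imbalance.
- A reader might infer that no result, positive or null, could be credited to the vehicle. For a positive result this does not follow. If Arm A did better on less drug, the dose difference would have worked against it and could not explain the benefit.
- A reader might take the 5 mg/5 mL on the sheet as further evidence that the arms differ. The sheet is common to both arms, so it bears on absolute dose and not on the contrast between arms.

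The sheet's figure may be a slip, but the documents do not identify it as one. It also calls the solution concentrated, which on its face implies a dilution that the steps omit.

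**Conclusion.** The documents contradict themselves on the strength of the study drug, in two ways.

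The conflict between Appendix 1 and the body is unconditional: a factor of ten in both arms, or 105 mg against 10.5 mg a week if the sheet is followed as written. It touches the safety reasoning in Sections 8.1 and 10.4. It does not show that any patient would receive the higher amount, because the body specifies the dispensed bottles at 0.5 mg/5 mL.

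The Arm A conflict is conditional. The commercial-solution description and the finished strength of 0.5 mg/5 mL cannot both hold unless dexamethasone is added at compounding, which the protocol does not describe. If none is added, Arm A delivers 0.5 × (1 − v) mg per rinse, and a null result could not be read as a test of the vehicle at equal dose. The size of any shortfall depends on v, which is not given. A missing vehicle fraction alone would be only an absent detail. The point matters because the stated strengths disagree while the hypothesis assumes that they are equal.

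**What to change.** - Reconcile Sections 2.2, 4.2, 5.2, 5.3, 11.1.4, 11.1.5 and 11.2.6 and Appendix 1 with the investigational pharmacy, so that one strength per arm as dispensed appears throughout. Which strength that is lies with the sponsor and the pharmacy.
- State the starting material of Arm A in Section 11.1.5, including any source of dexamethasone other than the commercial solution, and the share of vehicle in the finished rinse.
- Make the patient sheet agree with what is dispensed, and make its title and steps agree on whether the patient prepares anything.
- Check the weekly maximum in Sections 8.1 and 10.4 against the reconciled strength, and correct the gram unit there.
- If the strengths as dispensed differ between arms, reword Sections 2.4 and 2.5.1 to describe a comparison of two products, not of a vehicle at equal dose.

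The cost is wording, one confirmation from the pharmacy, and a protocol and patient-sheet amendment through the IRB under Section 6.3.2. Sample size, visits and analysis methods do not change.
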